1.0 Investigational Design

1.1.Study Design

This investigation is a randomized controlled trial of three techniques to evaluate clinically, radiographic, and histologically the efficacy of L-PRF with freeze-dried bone allograft (FDBA) layered technique in improving quantity and quality of new vital bone formation and alveolar ridge dimensional stability following ridge preservation in comparison to L-PRF alone and L-PRF/FDBA.

Control technique: Ridge preservation using L-PRF/FDBA and ridge preservation using L-PRF alone

Test technique: Ridge preservation using L-PRF/FDBA layered technique

1.2. Objectives:

- To evaluate clinical and radiographic dimensional changes at alveolar ridge 3 months after ridge preservation procedure using L-PRF alone, L-PRF/FDBA, and L-PRF/FDBA Layered technique.

- To evaluate quantity and quality of new vital bone in sockets 3 months after ridge preservation procedure using L-PRF alone, L-PRF/FDBA, and L-PRF/FDBA Layered technique.

1.3. Hypotheses and Specific Aims:

- **Hypothesis 1:** Ridge preservation using L-PRF/FDBA Layered technique will best preserve alveolar ridge dimensions in comparison to using L-PRF alone.
- **Hypothesis 2:** Ridge preservation using L-PRF/FDBA Layered technique will improve new vital bone formation at the middle and apical thirds of the socket in comparison to using L-PRF/FDBA.

• Specific Aims:

1. To compare quantitative clinical alveolar ridge dimensions (in mm) 3 months after ridge preservation between the three groups using an intraoral scan and direct clinical assessment.

- 2. To compare quantitative two- and three- dimensional radiographic alveolar ridge dimensional changes (in mm) 3 months after ridge preservation between the three groups using Cone Beam Computed Tomography (CBCT) and virtual implant planning software.
- 3. To compare qualitative and quantitative histologic characteristics of new bone between the three groups after 3 months of ridge preservation by quantifying the distribution (in %) of new vital bone, connective tissue, residual graft particles, and artifact at the healed socket site.

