Post-surgical analgesics will be prescribed and/or dispensed as deemed necessary by the treating surgeon and a continued course of antibiotic will be prescribed for a 1-day time of period. Written and oral home care instructions will be provided.

- Visit 2 (Follow-up visit): Sutures will be removed after two weeks. Surgical site will be evaluated for healing status and post-operative instructions on resuming oral hygiene measures will be given to patients. Medical history will be reviewed, and patients will complete a questionnaire regarding their assessment of the post-operative discomfort they experienced during the initial healing phase, including number of days of altered activity/discomfort and number of tablets of pain medications taken.
- Visit 3 (Follow-up visit): After four weeks, surgical site will be evaluated for healing status and oral hygiene instructions will be reinforced. Medical history will be reviewed, and adverse events will be record.

• Visit 4 (Surgical visit): Bone biopsy and implant placement

After three months, surgical site will be evaluated. A second intraoral scan will be taken to evaluate clinical ridge dimensions. A second CBCT scan will be taken to evaluate the dimensional changes of the healed socket and plan the optimal implant location using implant planning software. Medical history will be reviewed, and adverse events will be record.

A surgical approach will be performed to take a bone biopsy for research purposes and implant placement at the same site. The procedure will be performed under local anesthesia and IV conscious sedation if patient requested it. After a full-thickness mucoperiosteal flap will be raised, the ridge dimensions will be measured at the crestal bone for dimensional changes in height and width using a calibrated surgical caliper and UNC-15 periodontal probe. Prior to implant placement, a bone biopsy will be taken from the center of the new bone using a 2mm internal diameter trephine bur. The dimensions of the harvested bone core will be 2mm in diameter and the length will be according to the implant dimension to be placed. The biopsy will be stored in 10% neutral buffered formalin and will be sent to the Histomorphometry and Molecular Analysis Core in the UAB Lyons Harrison Building. The Implant preparation osteotomy site will be completed following manufacturer protocol.

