3.2.Visual Analog Scale (VAS) survey is a questionnaire regarding post-operative pain, swelling, bruising effect, and daily activities tolerance. For each question, patients are asked to mark on a 0 to 10 scale their perception of the level of corresponding pain, swelling, bruising, and alterations to daily activities with 0 being no symptoms and 10 being the worst symptom imaginable. It will be completed two weeks after every surgical procedure.

3.3.Outcomes measurements:

• Clinical and Radiographic Measurements:

Clinical measurements will be taken by one experienced blinded examiner to the randomization process before ridge preservation procedure and 3 months after ridge preservation, using intraoral scan and direct clinical assessment using a calibrated surgical caliper and UNC-15 periodontal probe (in millimeters). Another blinded examiner will perform the radiographic measurements at time of ridge preservation procedure and 3 months after ridge preservation, using a CBCT and implant planning software (in millimeters). Horizontal and vertical ridge dimensions will be evaluated clinically and radiographic. Intra-examiner calibration will be conducted to ensure reliability of measuring method.

• Histomorphometric Analysis:

Each specimen will be fixated with 10% neutral buffered formalin for 48 hours prior to be dehydrated and embedded in methylmethacrylate. It will be ground sectioned at the center of the biopsy in its long axis into 50-70 micron-thick sections (Exakt Technologies, Inc., Oklahoma City, OK), and polished with 4000 grit sandpaper and Novus Polish to create a surface as smooth as possible. All sections will be stained with Sanderson's Bone Stain and imaged for quantification of bone formation. Histomorphometry will be done using the Bioquant Image Analysis Software (R&M Biometrics, Nashville, TN) by measuring the total surface of vital bone, residual graft particles, organic matrix and artifact/air components. Corresponding percentages will be calculated for each of these tissues and compared between the three groups (L-PRF, L-PRF/FDBA, LPRF/FDBA layered technique). These experiments and measurements will be conducted by an experienced blinded lab technician.

3.4.Statistical Analysis:

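### Hypothesis 2 concerns vital bone in the middle and apical thirds of the socket, but the plan specifies no measurement or analysis by third and so does not test it

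*Combined protocol and SAP*

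**What the plan says.** Section 1.3 states Hypothesis 2 by region and by contrast: "Layered technique will improve new vital bone formation at the middle and apical thirds of the socket in comparison to using L-PRF/FDBA". The related objective and aim are not regional. Objective 2 (section 1.2) is "To evaluate quantity and quality of new vital bone in sockets 3 months after ridge preservation procedure", and Specific Aim 3 (section 1.3) is to be met by "quantifying the distribution (in %) of new vital bone, connective tissue, residual graft particles, and artifact at the healed socket site".

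Section 3.1 describes grafts that differ by level. Group 1 receives an L-PRF plug in the apical and middle thirds and sticky bone (FDBA, L-PRF pieces and fibrinogen) in the coronal third. Group 2 receives sticky bone along the socket. At Visit 4 one core is taken from the centre of the new bone, and "the length will be according to the implant dimension to be placed".

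Section 3.3 has each core "ground sectioned at the center of the biopsy in its long axis" and quantified "by measuring the total surface of vital bone, residual graft particles, organic matrix and artifact/air components". Then: "Corresponding percentages will be calculated for each of these tissues and compared between the three groups". Blinding is covered: "These experiments and measurements will be conducted by an experienced blinded lab technician". Section 3.4 names a t test or Wilcoxon test between groups, with no regional variable, and sizes the trial only on a 1.0 mm change in ridge dimensions.

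**The concern.** Hypothesis 2 is one of two hypotheses and the only histologic one. Its quantity is the Group 1 minus Group 2 difference in vital bone at the two levels where the arms receive different material. The quantity that section 3.3 appears to produce is a percentage over the whole core, which mixes those levels with the coronal third, where both arms receive sticky bone.

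If the trial is run as written, the report would have no estimate for the claim in Hypothesis 2. A whole-core difference could be presented as support for a regional benefit that was never measured, or a whole-core null could hide a regional benefit. A by-third reading added later would have no level boundaries fixed in advance and, unless the cores were marked at harvest, no assured orientation.

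**Working it through.** **1. Text comparison.**

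| Place | Region | Quantity |
|---|---|---|
| 1.3, Hypothesis 2 | middle and apical thirds | new vital bone, layered vs L-PRF/FDBA |
| 1.2, Objective 2 | socket | new vital bone, three groups |
| 1.3, Aim 3 | healed socket site | % of each tissue, three groups |
| 3.1, graft placement | thirds named | material placed, not an outcome |
| 3.1, Visit 4 | core length set by the implant | no rule for orientation or for reaching the apical third |
| 3.3, histomorphometry | none named | total surface and % of each tissue |
| 3.4, statistics | none named | between-group tests; power for ridge dimension only |

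Outside Hypothesis 2, thirds of the socket appear only in the graft-placement text. Nothing turns them into an endpoint.

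**2. What a whole-core difference can and cannot show.** Assume each core holds the three thirds in equal parts. Let R be the Group 1 minus Group 2 difference in the middle/apical region and C the difference in the coronal third, both in percentage points. Then

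D(whole) = (C + 2R) / 3.

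| R | C | D(whole) |
|---|---|---|
| +15 | 0 | (0 + 30)/3 = +10 |
| +10 | +10 | (10 + 20)/3 = +10 |
| 0 | +30 | (30 + 0)/3 = +10 |
| 0 | 0 | 0 |
| +10 | -20 | (-20 + 20)/3 = 0 |

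The same whole-core result fits different values of R, including zero. A larger sample does not remove this. Core length follows the implant and not the socket depth, so the weights 1/3 and 2/3 may also vary between patients. The documents give neither length, so how much they vary is unknown.

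**3. Power, as an illustration only.** The plan's one sample-size figure, 10 per group for 1.0 mm, concerns ridge dimension, and no SD is stated, so it can be neither reproduced nor carried over to vital bone. Assume instead equal thirds, equal SDs, a common correlation r between thirds, k = C/R, n = 10 per group and two-sided alpha 0.05. By the noncentral t (18 df), a standardized regional effect of 1.325 has 80% power. The whole-core effect is the regional effect multiplied by

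((2 + k)/3) × √((1 + r)/2) / √((1 + 2r)/3).

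| k | r | Ratio | Whole-core effect | Power |
|---|---|---|---|---|
| 0 | 1 | 0.667 | 0.883 | 46% |
| 0 | 0.5 | 0.707 | 0.937 | 51% |
| 0 | 0 | 0.816 | 1.082 | 63% |
| 1 | 1 | 1.000 | 1.325 | 80% |
| 1 | 0.5 | 1.061 | 1.405 | 84% |
| 1 | 0 | 1.225 | 1.623 | 93% |

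The whole core has lower power than the region only when k is below 1.00, 0.83 or 0.45 at r = 1, 0.5 or 0. The direction of the power effect is therefore not fixed. If the Bonferroni sentence in 3.4 means 0.05/5 = 0.01, a regional effect of 1.686 has 80% power; the k = 0, r = 1 case then gives 38.5%, and k = 1, r = 1 again gives 80%.

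**The case against.** The best defence is that the plan is silent on regions but does not exclude them. Total surface may only mean the summed area of each tissue, and a long-axis section keeps the levels in order if the core stays intact and its orientation is known. This stands as an argument that a by-level reading is feasible, which is why the fix is cheap. It does not make the reading planned: no level, boundary, orientation mark or regional test is stated.

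A second point is that both arms receive sticky bone coronally, so the coronal difference may be small and a whole-core difference would then mainly reflect the middle and apical region. This has weight. It makes splits such as 0 with +30 less plausible than +15 with 0, and the whole-core result is indirect evidence rather than none. But coronal equality is not assured. The 50%-50% mix is stated only for Group 1, and healing may differ by level.

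Third, the 46% figure is the lowest power for k = 0 over r from 0 to 1, and power can rise in other cases. That is correct; the conclusion does not rest on power. It is also fair that the documents do not show that cores miss the apical third; that is a possibility only.

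**Conclusion.** The concern holds. The measurement specified does not match Hypothesis 2, and following the plan as written gives no direct estimate or test of it. This rests on reading section 3.3 as one percentage per tissue per core, which is the natural reading; under any reading, a by-third analysis is unspecified. The percentage-point examples rest on the equal-thirds assumption, but the ambiguity they show arises for any core that mixes coronal and deeper bone. The size of the effect on power cannot be given from the documents.

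This should be fixed, ideally before the first biopsy, because orientation is best recorded at harvest. The problem is confined to Hypothesis 2: Hypothesis 1, the ridge-dimension aims, Objective 2 and Aim 3 stand as they are.

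**What to change.** Either of two changes closes the gap.

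**Measure by level (preferred if Hypothesis 2 is to be kept).** In sections 3.1 and 3.3:

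1. Mark the coronal end of each core at harvest.
2. Have the blinded technician record vital bone % by level on the existing long-axis sections, with levels set from socket depth on the post-extraction CBCT and bone beyond the original socket excluded.
3. In 3.4, name the Group 1 vs Group 2 comparison of vital bone % in the middle and apical region as the test of Hypothesis 2. Report the middle and apical thirds separately as well, keep the whole-core percentage for Aim 3, and say how the regional test relates to the Bonferroni statement.
4. For cores that do not reach the full apical third, report number and length by group, and add a sensitivity analysis limited to cores that cover the region.

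The cost is protocol wording, one mark per core, a depth reading from a scan already taken and some image-analysis time. No extra biopsy, scan, section or stain is needed. The downsides are real. The mapping is approximate, because the crest may change over 3 months and the trephine path may not follow the socket axis. Regional percentages may be more variable than whole-core ones, and short cores may leave fewer than 10 per group in the sensitivity analysis.

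**Reword.** If regional measurement is not feasible, restate Hypothesis 2 as whole-core vital bone % and draw no conclusion by third. This costs only wording, but gives up the regional claim.

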3.0 Study procedures

3.1 Summary of study procedures

• Screening/baseline visit: Upon enrollment into the study the patient's medical history and electronic records will be reviewed. Patients will be treatment planned by an interdisciplinary team consisting of a surgeon and a prosthodontist or restorative dentist. Clinical examiners will conduct clinical and radiographic exams to determine eligibility according to the above inclusion criteria. An intraoral scan will be taken to perform clinical measurements. Study visits and objectives will be explained to all participants. IRB approved written informed consent will be obtained from all the participants.

• Visit 1 (Surgical visit): Extraction and ridge preservation

• **Randomization:** Participants will be stratified and randomized to one of three treatment groups: Table 1, by permuted block randomization approach to ensure same number of patients in each group, using computer-generated random number list.

Table 1. Groups of treatment	
------------------------------	--

Group	Treatment	Number of participants
Group 1	Atraumatic tooth extraction followed by ridge preservation using	10
	Leucocyte and Platelet Rich Fibrin (L-PRF) + Freeze-Dried Bone	
	Allograft (FDBA) Layered technique	
Group 2	Atraumatic tooth extraction followed by ridge preservation using	10
	Leucocyte and Platelet Rich Fibrin (L-PRF) + Freeze-Dried Bone	
	Allograft (FDBA)	
Group 3	Atraumatic tooth extraction followed by ridge preservation using L-	10
	PRF	

• **Surgical procedure:** A loading dose of prophylactic antibiotic will be dispensed (Amoxicillin 2 grs or Clindamycin 600mg, 30 minutes to one hour prior to the surgery). Venous blood will be drawn (antecubital fossa) with a 25-butterfly needle to fill 4-8 collection tubes of 10ml each. The tubes will not contain any additive or anticoagulant. One tube will be centrifuged for 3 minutes and the other tubes will be centrifuged for 12 minutes. After centrifugation, L-PRF clots will be collected and stored in a closed sterile storage container that enables compression of clots into membranes/plugs. Additionally, the one tube that received less centrifugation (fibrinogen) will be used as an additive with the L-PRF membranes and bone allograft. The bone graft material utilized for patients in group 2 and 3 will be MinerOss cortico-cancellous freeze-dried bone allograft (FDBA).

L-PRF Preparation			

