A power analysis was conducted to determine the sufficient number of patients in each treatment group to obtain a power of 80% to detect a 1.0mm change in ridge dimensions using a type 1 (alpha) error rate of 0.05. The power analysis determined that a minimum of 10 patients would be required for each group, and 30 patients in total. An alpha of 0.05 was assumed after a Bonferroni correction for five relevant 2-way comparisons between the treatment groups.

Two-tailed *t* test will be used to compare clinical characteristics between patients with the L-PRF/FDBA layered technique, L-PRF/FDBA, and those with L-PRF alone for continuous variables with a normal distribution. Nonparametric (Wilcoxon) test will be used otherwise.

For categorical variables, inter-group comparisons will be conducted using chi-square test or Fisher's Extract Test, as deemed necessary. To determine whether the groups experienced equivalent changes in bone growth from baseline to follow-up, paired *t* (or Wilcoxon signed-rank) and Mc Nemar's tests will be used for continuous and categorical variables, respectively.

The α level will be set at 0.05. Statistical analysis will be carried out using SAS software version 9.4 (SAS Institute, Inc, Cary, North Carolina).

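### The plan claims a Bonferroni correction for five between-group comparisons that it never lists, and its analysis text then tests at an unadjusted 0.05

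*Combined protocol and SAP*

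**What the plan says.** Multiplicity is mentioned once, in the sample-size paragraph of section 3.4. The trial is sized "to obtain a power of 80% to detect a 1.0mm change in ridge dimensions using a type 1 (alpha) error rate of 0.05", and the paragraph ends: "An alpha of 0.05 was assumed after a Bonferroni correction for five relevant 2-way comparisons between the treatment groups".

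The design has three arms. Section 3.1 says "Participants will be stratified and randomized to one of three treatment groups", and Table 1 lists three groups of 10. Section 1.1 names one test technique and two controls. Section 1.3 has two hypotheses, each with one directed contrast. Hypothesis 1 reads "Ridge preservation using L-PRF/FDBA Layered technique will best preserve alveolar ridge dimensions in comparison to using L-PRF alone". Hypothesis 2 compares the layered technique with L-PRF/FDBA on new vital bone. Section 3.3 adds that "Horizontal and vertical ridge dimensions will be evaluated clinically and radiographic".

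The analysis paragraphs of section 3.4 say that a two-tailed t test (Wilcoxon if not normal) "will be used to compare clinical characteristics between patients with the L-PRF/FDBA layered technique, L-PRF/FDBA, and those with L-PRF alone for continuous variables". They mention neither Bonferroni, nor an adjusted level, nor a family of tests, and they close with "The α level will be set at 0.05".

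**The concern.** The number of comparisons fixes the Bonferroni divisor, and the divisor fixes the threshold at which a group difference is declared. Here the number matches nothing countable in the design, and the correction does not reach the text that governs the tests.

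Saying that 0.05 applies after the correction can mean two things. It may be the level for each test, or the overall level, in which case each test uses something smaller. The same p value then gets different verdicts:

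- p = 0.03 is positive at 0.05 and negative at 0.025 or 0.0167.
- p = 0.02 is positive at 0.025 and negative at 0.0167.
- p = 0.012 is positive with three comparisons (0.0167) and negative with five (0.01).

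As written, the rule could be settled after the results are known. It is also unclear which per-test alpha the 80% power refers to.

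**Working it through.** **Inputs from the documents.** Three groups of 10 (section 3.1, Table 1); two-tailed two-group tests, alpha 0.05, power 80%, effect 1.0 mm, five comparisons claimed (section 3.4). No SD is given.

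**Assumptions.** The t tests in section 3.4 are the between-group outcome comparisons. This has to be assumed because the only sentence there on change over time ("To determine whether the groups experienced equivalent changes in bone growth from baseline to follow-up") names paired tests. Data are normal with equal variances, and 1.0 mm is a between-group difference.

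**1. The count.** Pairs among three groups: 3 × 2 / 2 = 3. Four groups would give 6, so no number of groups gives five. Test-versus-control pairs: 2. Contrasts named in the hypotheses: 2.

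**2. Per-test alpha by family size.**
- Two comparisons: 0.05/2 = 0.025
- Three: 0.05/3 = 0.0167
- Five: 0.05/5 = 0.01

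If instead 0.05 is the per-test level, the Bonferroni bound on the family is 3 × 0.05 = 0.15 for three tests and 5 × 0.05 = 0.25 for five.

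**3. Family-wise error for one outcome.** The three pairs share groups, so the tests are correlated and the bound is not reached. Simulation of 1,000,000 trials, all groups equal, 10 per group, two-sample t with 18 df:

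| Comparisons on one outcome | Per-test alpha | Chance of at least one false positive |
|---|---|---|
| Three pairs | 0.05 | 12.3% |
| Three pairs | 0.0167 | 4.4% |
| Three pairs | 0.01 | 2.7% |
| Two test-versus-control pairs | 0.05 | 9.1% |

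With the Wilcoxon test (exact critical value, 100,000 trials), three pairs at 0.05 give 10.7%.

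**4. Can the sample size show which alpha was used?** The plan's figure of 10 per group cannot be reproduced without an SD, so I solved for the SD that makes it correct. Power is P(T > t₁₋α/₂,₁₈), with T noncentral t on 18 df and noncentrality 1.0 / (SD × √(2/10)). Setting power to 80%:

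| Per-test alpha | Largest SD giving 80% power at 10 per group |
|---|---|
| 0.05 | 0.755 mm |
| 0.025 | 0.674 mm |
| 0.0167 | 0.635 mm |
| 0.01 | 0.593 mm |

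Ten per group fits every reading with a suitable SD. It neither identifies the alpha nor is shown to be wrong.

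**5. What a stricter alpha would do to power.** Suppose 10 per group was sized at a per-test 0.05, so SD = 0.755 mm and the noncentrality is 1.0 / (0.755 × 0.447) = 2.96. Then:

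| Per-test alpha | Power at 10 per group | Per group for 80% |
|---|---|---|
| 0.05 | 80% | 10 |
| 0.025 | 70% | 13 |
| 0.0167 | 63% | 14 |
| 0.01 | 55% | 16 |

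If the trial was already sized at the stricter level, nothing is lost.

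**The case against.** The strongest reply is that the sentence speaks of relevant comparisons and does not say they are all the pairs. Comparisons made on several outcomes are still between treatment groups. Section 3.3 has four ridge measures (horizontal and vertical, clinical and radiographic), and vital bone from Hypothesis 2 would make five. On that view the plan intends multiplicity control, and the closing alpha of 0.05 is simply the overall level.

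Part of this stands. A reader might infer that five is impossible with three groups. The documents do not support going that far, because a count across outcomes is conceivable. But no section defines such a family, says which pair would be tested on each outcome, or gives a per-test threshold. The reply changes the fault from a proven miscount to an undefined family, and the threshold stays undetermined.

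It is also fair that the 12.3% depends on reading the analysis text literally, without the correction, and on testing all three pairs. The plan nowhere declares that family. Still, literal reading is what a written analysis plan is for, and even the two test-versus-control pairs alone give 9.1%.

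**Conclusion.** The point holds. The stated count matches neither the three pairs nor the two hypothesis contrasts, no list explains it, and the analysis text does not carry the correction. Followed as written, that text gives a family-wise error of about 12.3% per outcome instead of the 5% that a Bonferroni correction would imply. This rests on the assumptions listed in the working: the t tests are the outcome comparisons, all three pairs are tested, and data are normal with equal variances.

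Two stronger readings are not supported. One is that the trial is underpowered or that 10 per group is wrong: with no SD in the documents, this cannot be tested. The other is that the plan must reduce to a single confirmatory contrast. Section 1.3 does not rank Hypothesis 2 below Hypothesis 1, so that choice belongs to the sponsor.

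**What to change.** In section 3.4:

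1. Replace the count of five with a list of the comparisons in the family, and name the ridge dimension and measurement method concerned. Either of these families fits the design:
   - the three pairs on that dimension, each tested at 0.05/3 = 0.0167; or
   - the Hypothesis 1 contrast on that dimension and the Hypothesis 2 contrast on vital bone, each tested at 0.05/2 = 0.025. This keeps both stated hypotheses confirmatory.
2. State that per-test alpha in both the power paragraph and the analysis paragraphs, in place of the bare 0.05.
3. Label all other pairs and outcomes exploratory, with no family-wise error claim.
4. Restate the power at that alpha, giving the SD used.

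The edit is to wording only, but the stated power may fall. If 10 per group was sized at a per-test 0.05 (assumed SD 0.755 mm), power for 1.0 mm is about 70% at 0.025 and 63% at 0.0167. Restoring 80% would then take 13 per group (39 in total) or 14 per group (42 in total). The sponsor can instead keep 30 patients and report the lower power openly. Comparisons outside the chosen family lose confirmatory status.

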Venous blood collection	Centrifuge white-covered tube for 3 minutes and red- covered tubes for 12 minutes	White-covered tubes: Fibrinogen Red-covered tubes: L-PRF membranes	

After preparation and isolation of the surgical area, local anesthesia will be accomplished by infiltration and/or intraoral nerve block. Intravenous moderate conscious sedation or inhalation sedation will be used in patients who requested it.

Tooth or teeth will be gently elevated using a minimally traumatic technique that prevent loss of supporting bone. Socket(s) will be curetted, irrigated with saline, and inspected following extraction and verified for the presence of intact walls.

A Cone Beam Computed Tomography (CBCT) scan will be taken immediately after the tooth extraction, before ridge preservation procedure. It will serve for baseline radiographic measurements.

Group 1: L-PRF/FDBA Layered technique:

After socket is cleaned, a L-PRF plug will be formed, placed and compacted at the apical and middle third of the socket. Two membranes of L-PRF will be cut into small pieces and combined with 0.5 cc of cortico-cancellous bone allograft (FDBA), in a 50%-50% proportion, and fibrinogen forming sticky bone. The sticky bone will be placed and compacted at the coronal third of the socket (over the L-PRF plug already placed). A membrane of L-PRF will be placed at the coronal extent of the socket, flaps will be reapproximated and sutured with Monocryl 5-0 sutures.

Group 1: L-PRF/FDBA Layered technique	
	LPRF membranes

	L-PRF plug formed and placed in the apical and middle third of the socket
	L-PRF membrane chopped into small pieces and combined with FDBA and fibrinogen forming sticky bone
	Sticky bone is placed at the coronal third of the socket (over the L-PRF plug)

Group 2: L-PRF/FDBA:

After socket is cleaned, L-PRF membranes will be chopped into small pieces and combined with 0.5 cc of cortico-cancellous bone allograft (FDBA) and fibrinogen forming sticky bone. The sticky bone will be placed and compacted at the along the socket. A membrane of L-PRF will be placed at the coronal extent of the socket, flaps will be reapproximated and sutured with Monocryl 5-0 sutures.

Group 3: L-PRF

After the socket is cleaned, the socket will be completely filled with L-PRF plugs and a L-PRF membrane will be placed at the coronal extent of the socket, flaps will be reapproximated and sutured with Monocryl 5-0 sutures.

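### The between-group tests make no use of the measured baseline ridge dimension, and section 3.4 does not say whether the 3-month value or the change is tested

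*Combined protocol and SAP*

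**What the plan says.** **Between-group test.** Section 3.4 says a two-tailed t "test will be used to compare clinical characteristics between patients with the L-PRF/FDBA layered technique, L-PRF/FDBA, and those with L-PRF alone", with a Wilcoxon test when the data are not normal. It names no covariate and no model covering all three groups. Baseline enters the section only through paired t, signed-rank or McNemar tests. Those work within a group, although the text offers them as a way to judge whether the groups changed equivalently.

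**Baseline data.** Section 3.3 has clinical ridge measurements taken before the procedure and again at 3 months. Of the CBCT taken right after extraction, section 3.1 says "It will serve for baseline radiographic measurements". Table 2 schedules clinical and radiographic ridge assessments at both V1 and V4.

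**Outcome wording.** Aim 1 (section 1.3) reads "To compare quantitative clinical alveolar ridge dimensions (in mm) 3 months after ridge preservation between the three groups". Objective 1 (section 1.2) reads "To evaluate clinical and radiographic dimensional changes at alveolar ridge 3 months after ridge preservation procedure". Aim 2 and the Visit 4 caliper and probe text in section 3.1 also speak of dimensional change. The power statement is framed "to detect a 1.0mm change in ridge dimensions".

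**The concern.** Section 2.1 admits any hopeless single-rooted tooth whose socket keeps four walls, so patients can differ in ridge size before treatment. With 10 per group, some of that difference will fall unevenly between arms by chance. A test on raw 3-month values carries all of it as noise. A test on change subtracts the baseline in full, which over-corrects when the correlation between baseline and 3-month values is below 1. A model with baseline as a covariate estimates how much to subtract.

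Two things are at stake. One is power, in a trial sized at its own stated minimum. The other is that section 3.4 lets an analyst defend either the raw value or the change as the tested variable, so the choice could be made after results are seen.

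**Working it through.** **Inputs from section 3.4:** 10 per group, 30 in total; target 1.0 mm; power 80%; two-sided alpha 0.05. **Not given:** the SD and the baseline to 3-month correlation (rho). Rho is assumed at 0.5, 0.7 and 0.9. Dropout is taken as nil.

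**Step 1. The plan's own figure.** Without an SD, 10 per group can be neither reproduced nor refuted; one can only solve for the SD it implies. For a two-group t test with 18 df, the noncentrality is 1.0 / (SD × √(2/10)). The critical value is 2.101, and 80% power needs a noncentrality of 2.963, so SD = 1.0 / (2.963 × 0.4472) = 0.755 mm. The plan adds: "An alpha of 0.05 was assumed after a Bonferroni correction for five relevant 2-way comparisons between the treatment groups". If that means 0.05/5 = 0.01 per test, the critical value is 2.878, the noncentrality 3.770 and the SD 0.593 mm.

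**Step 2. Link the three analyses.** Take 0.755 mm as the SD of change, since the power statement speaks of change. Write σ for the SD of the raw dimension at each time.

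- Change: SD = σ√(2(1 − rho)), so σ = 0.755 / √(2(1 − rho)).
- Baseline-adjusted: residual SD = σ√(1 − rho²) = 0.755 × √((1 + rho)/2).

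**Step 3. Power for 1.0 mm at two-sided 0.05.** The raw and change tests use 18 df. The three-arm ANCOVA uses 30 − 3 − 1 = 26 df, with the contrast variance multiplied by 1 + 1/25 for estimating the covariate slope.

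| | rho 0.5 | rho 0.7 | rho 0.9 |
|---|---|---|---|
| Raw SD σ (mm) | 0.755 | 0.974 | 1.688 |
| Residual SD (mm) | 0.654 | 0.696 | 0.736 |
| t test on raw 3-month value | 80% | 58% | 24% |
| t test on change | 80% | 80% | 80% |
| Three-arm ANCOVA | 90% | 86% | 82% |

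**Step 4. Separate adjustment from pooling.** Comparing change scores with error pooled over three arms (27 df) gives 81.5%. Of the ANCOVA gain over the pairwise change-score test (about 10, 6 and 2 points), about 1.5 points therefore come from pooling. Adjustment itself adds about 8, 4 and 0.3 points.

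**Step 5. Other assumptions.**

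- At rho 0.3, with the SD of change still 0.755 mm: raw 91%, change 80%, two-arm ANCOVA 93%. Simply choosing change is therefore not a safe repair.
- If 0.755 mm is instead the raw SD: raw 80%; two-arm ANCOVA (17 df) 90% at rho 0.5 and 97% at 0.7. At rho 0 it gives 79.7%, so an uninformative baseline costs almost nothing.
- At alpha 0.01 with SD of change 0.593 mm, the same formulas give raw 80%, 53% and 15%; change 80%; three-arm ANCOVA 92%, 88% and 83%.

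**The case against.** The strongest reply is that the plan intends change throughout. Objective 1, Aim 2 and the power statement say so. So does the Visit 4 text, which concerns the same caliper and probe measure that Aim 1 covers; Aim 1 may simply be loosely worded. On that reading starting ridge size is already subtracted, and adjustment adds little where the correlation is high. With an allowance for estimating the slope, a two-arm ANCOVA at rho 0.9 gives about 79%, no better than the 80% of the change-score t test.

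Much of this stands. A reader might infer from Aim 1 that raw 3-month values will be tested and that power could fall to 24%. The documents do not settle that reading, and most of their wording points the other way. A reader might also infer that anatomical differences bias the comparison. They do not: under randomization the unadjusted test is valid, and baseline anatomy adds only noise and chance imbalance. Section 3.1 also mentions stratification without naming the factors, so some protection against imbalance may exist that the calculations above do not credit.

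What does not fall away is the text of section 3.4. It never says that change is the variable tested between groups, it uses no baseline covariate, and its paired tests do not compare groups.

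**Conclusion.** The point holds as a matter of precision and of an unspecified outcome variable, not of bias. Measured baselines are left out of every between-group test, and the tested variable needs to be reconciled between Aim 1 and the rest of the plan.

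On the more plausible change reading, a three-arm ANCOVA gains about 10, 6 or 2 points of power at rho 0.5, 0.7 or 0.9, including about 1.5 points from pooling. The larger losses, down to 58% and 24%, arise only if Aim 1 is taken literally and the correlation is 0.7 or 0.9.

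The direction is firm for any useful correlation. The size is not, because the SD is back-solved, the correlation is assumed, and the per-test alpha can be read two ways. The change is worth making because it is nearly free and the trial has no stated margin. The point covers ridge-dimension outcomes only; histology has no baseline.

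**What to change.** In section 3.4, for ridge-dimension outcomes, replace the pairwise t tests with one linear model over all 30 patients: 3-month value on treatment (three levels) plus the baseline value of the same measure.

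- Take the layered versus L-PRF and layered versus L-PRF/FDBA contrasts from that model, with 95% CIs, at the plan's multiplicity level. State in the same edit whether that level is 0.05 or 0.01 per test.
- Section 2.1 allows more than one qualifying tooth. Use one site per patient, or a patient-level random effect if several are treated.
- Keep a rank-based version as the fallback for non-normal data.
- Name the baseline for each measure, since Table 2 marks clinical ridge assessment at both Screening and V1.
- Reword Aim 1 to baseline-adjusted 3-month dimension, so that it agrees with Objective 1 and Aim 2.

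The cost is protocol and SAP wording, plus one degree of freedom per covariate. No new data or visits are needed. The edit should be made before outcome data are seen.
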